7.9.2 Secondary Efficacy Endpoint(s)

Other continuous change from Baseline endpoints will be analyzed using MMRM in the same manner as the primary endpoint (as described in section 7.9.1), but without control for multiple doses.

The change from Baseline on the BNSS total (12-item, excluding item 4) will be analyzed using MMRM in the same manner as the primary endpoint, but without control of multiple doses. The same analysis will be repeated on the change of Baseline on the BNSS total (13-item).

The change from Baseline on the CGI-SCH-S at Day 84, and the CGI-SCH-I score at Day 84 will be analyzed using a Cochran-Mantel-Haenszel test. This analysis will be stratified by age and performed using observed cases only.

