5.1.2 Secondary Objectives

- To determine whether add-on TAK-831 is superior to placebo on the Brief Negative Symptom Scale (BNSS) total score.
- To determine whether add-on TAK-831 is superior to placebo on the Brief Assessment of Cognition in Schizophrenia (BACS) composite cognition score.
- To determine whether add-on TAK-831 is superior to placebo on global severity as measured by the Clinical Global Impression-Schizophrenia-Severity (CGI-SCH-S) score.
- To determine whether add-on TAK-831 is superior to placebo on global improvement as measured by the Clinical Global Impression-Schizophrenia-Improvement (CGI-SCH-I) score.
- To determine whether add-on TAK-831 is superior to placebo on the Schizophrenia Cognition Rating Scale (SCoRS) assessment of cognitive functional outcome.
- To determine whether add-on TAK-831 is superior to placebo on the Positive and Negative Syndrome Scale (PANSS) total score and additional subscales and factors.
- To assess the safety and tolerability of TAK-831.
- To assess the PK of TAK-831.

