8. The subject is receiving primary background antipsychotic therapy (other than clozapine) at a total daily dose between 2 mg and 6 mg of risperidone equivalents (as outlined in an Antipsychotic Reference document supplied to the sites). Concomitant treatment with a subtherapeutic dose of a second antipsychotic may be permitted with sponsor or designee approval if used to treat specific symptoms, such as insomnia (for example, quetiapine 100 mg or its equivalent once daily at bedtime) or anxiety (for example, quetiapine 25-50 mg or its equivalent as needed for anxiety), but not if it is used for refractory positive psychosis symptoms. Under this exception, the total daily dose of the second antipsychotic will not have to be included in the calculation of the 6 mg/day risperidone-equivalent limit. Recognizing that some prescribers use higher doses of quetiapine as a hypnotic, subjects taking up to 200 mg quetiapine or its equivalent as a hypnotic may be enrolled after

- discussion with and approval from the sponsor or designee. Under this circumstance, the dosage above 100 mg quetiapine equivalent must be included in the calculation of the 6 mg/day risperidone-equivalent limit.
- 9. The subject is treated with a stable regimen of psychotropic medications with no clinically meaningful change (no increase in dose, ≤25% decrease in dose for tolerability) in the prescribed dose for 2 months before the screening visit, and no dose adjustment is anticipated throughout study participation up to the Day 84/early termination visit. As an exception, prohibited medications that are used as hypnotics or anxiolytics may be replaced with permitted medications as medically appropriate with approval from the sponsor or designee. Recognizing that physicians outside of the study may be managing the subject's background antipsychotic and other psychotropic medications, changes in background medication dosing that exceed this limit during the conduct of the study should be discussed with the sponsor or designee to determine subject disposition (based on consideration of safety and the study scientific objectives).
- 10. The subject has a BNSS total score (12-item, excluding number 4) ≥28; stable single-blind placebo run-in and baseline BNSS total (12-item, excluding number 4) scores (≤20% change from the screening score).

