9.1.10.3 CGI-SCH Scale

The CGI-SCH scale is an adapted version of the CGI scale that is designed to assess global illness status in patients with schizophrenia [23]. The assessment consist of 2 subscales, the CGI-

SCH-S and the CGI-SCH-I, which assess global severity of illness and change in the clinical condition over time, respectively, on a 7-point scale.

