13.1.3.2 Analysis of Other Efficacy Endpoints

Other change from baseline endpoints will be analyzed in the same manner as the primary endpoint, but without control for multiple doses.

The change from baseline on the CGI-SCH-S at Day 84, and the CGI-SCH-I score at Day 84 will be analyzed using a Cochran-Mantel-Haenszel test. This analysis will be stratified by age and performed using observed cases only.

For BNSS, BACS, CGI-SCH-I, CGI-SCH-S, SCoRS, PANSS total score and additional subscales and factors, the degree of impact from COVID-19 on completeness or collection modality will be assessed before unblinding the data. If the impact on an endpoint is deemed minimal, which is defined as less than 5% of the enrolled subjects having remote or missing final assessments due to COVID-19, then the original analysis plan will be followed. If there is more than a minimal impact, then a more thorough blinded review will be performed. After the blinded assessment, if substantial changes to the statistical analyses are needed to address the impact, the SAP will be amended before study unblinding. Minor changes may be documented in the clinical study report.

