7.0 METHODS OF ANALYSIS AND PRESENTATION

7.1 General Principles

Baseline values are defined as the last observed value before the first dose of study medication.

All statistical analyses will be conducted using SAS[®] Version 9.4, or higher, unless otherwise noted.

All confidence intervals, statistical tests, and resulting P-values will be reported as 2-sided and will be assessed at α =0.05 significance level unless otherwise stated. P-values will be rounded to 3 decimal places prior to assessment of statistical significance.

Means and medians will be presented to 1 more decimal place than the recorded data. The standard deviations (SDs) will be presented to 2 more decimal places than the recorded data. Confidence intervals about a parameter estimate will be presented using the same number of decimal places as the parameter estimate.

Where appropriate, variables will be summarized descriptively by study visit. For the categorical variables, the count and proportions of each possible value will be tabulated by treatment group. The denominator for the proportion will be based on the number of subjects who provided non-missing responses to the categorical variable. For continuous variables, the number of subjects with non-missing values, mean, median, SD, minimum, and maximum values will be tabulated.

Screen failure subjects will be grouped and listed at the end.

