7.9 Efficacy Analysis

The analyses and summaries for efficacy will be based on the FAS, unless otherwise noted.

7.9.1 **Primary Efficacy Endpoint(s)**

The primary endpoint is the change from Baseline on the PANSS NSFS at Day 84. The details of PANSS NSFS calculation can be found in Section 7.9.4.

The primary endpoint will be analyzed by comparing TAK-831 and placebo over all assessed time points using estimates from a mixed model for repeated measures (MMRM) with Baseline value as a covariate; pooled site, visit, treatment, and categorical age (randomization factor) as fixed factors; and treatment-by-visit and Baseline-by-visit interactions. Based on a Missing at Random Assumption, this analysis will be performed using observed case data only. The effect at each time point for each treatment is allowed to vary freely and an unstructured covariance matrix is assumed. If the model does not converge, other covariance structures (unstructured, compound symmetry, 2-Toeplitz, etc) will be considered.

Multiplicity will be controlled across dose-arms by first testing the 125 mg QD and 500 mg QD dose-arms in parallel using Holm's method to control the overall type I error rate at the 0.10 level (one-sided), then testing the 50 mg QD dose-arm at the 0.10 level if at least 1 of other doses is found to be statistically superior to placebo.

In order to provide additional insight about dose-response, the primary endpoint may be analyzed using a Multiple Comparison Procedure-Modeling (MCP-Mod) approach (Pinheiro et al, 2014).

For MCP-Mod approach, DoseFinding package in R statistical analysis software will be used. R has been validated by the contract research organization for this study. The following set of models will be fit to detect a dose response: linear, E_{max} , quadratic, and exponential. The stratification factor of age (<35 and \geq 35 years) will be included in the models. Each of the dose-response shapes in these models will be evaluated using optimal contrasts and applying MCP-Mod techniques to preserve the family-wise error rate (FWER) with the overall 1-sided significance level of 0.10. The effective dose(s) will be determined within this framework. The stratification factor of age may be omitted if the dose response for the stratified models cannot be reliably estimated.

The following supplementary analyses will also be conducted for the primary endpoint:

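### The Day 84 test of change in CGI-SCH-S leaves out the Day 1 score as a covariate, which gives up some precision on a secondary endpoint (minor)

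*SAP*

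**What the plan says.** SAP section 7.9.2 treats both Day 84 CGI outcomes, the CGI-SCH-S change and the CGI-SCH-I rating, alike: each "will be analyzed using a Cochran-Mantel-Haenszel test. This analysis will be stratified by age and performed using observed cases only". Protocol section 13.1.3.2 agrees: "This analysis will be stratified by age and performed using observed cases only". The protocol synopsis says the same. The age strata are the two randomisation strata, under 35 and 35 or over.

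The remaining continuous change endpoints follow the primary analysis in SAP section 7.9.1, a "mixed model for repeated measures (MMRM) with Baseline value as a covariate", with a baseline-by-visit interaction.

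The schedule in Protocol Appendix A collects CGI-SCH-S on Day 1, which is the baseline, and again on Days 28, 56 and 84. Protocol section 9.1.10.3 describes the two subscales, "which assess global severity of illness and change in the clinical condition over time, respectively, on a 7-point scale". Protocol section 5.1.2 attaches an objective to the severity score: to show that add-on TAK-831 is "superior to placebo on global severity as measured by the Clinical Global Impression-Schizophrenia-Severity (CGI-SCH-S) score".

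No level is given for the CGI tests, so the default in SAP section 7.1 applies: "statistical tests, and resulting P-values will be reported as 2-sided and will be assessed at" 0.05.

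**The concern.** A change score uses the baseline by subtracting it with a fixed coefficient of one. That is fully efficient only when the regression of the Day 84 score on the Day 1 score has slope one. If the slope is lower, the change score still carries baseline variation that a covariate would remove. The plan removes it for the other continuous change endpoints but not for CGI-SCH-S, although the Day 1 value is in the database.

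At stake is the chance of detecting an effect on global severity, which has its own superiority objective. In a phase 2 study that result helps in reading the primary finding, but it is not part of the controlled testing sequence.

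**Working it through.** **The plan's own figure.** The only stated power is at least 82% for the primary endpoint. With 85% completion, the numbers at Day 84 are 0.85 × 52 = 44.2 on a dose and 0.85 × 78 = 66.3 on placebo. The noncentrality at effect size 0.4 is 0.4 × √(44.2 × 66.3 / 110.5) = 0.4 × √26.52 = 2.06. The first Holm step is one-sided 0.05 (critical value 1.645), so power per dose is Φ(2.06 − 1.645) = 66.1%. The two tests share placebo and correlate at 44.2 / 110.5 = 0.40, so power for at least one dose is 82.8%. The stated 82% is reproduced and does not depend on the CGI analysis.

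**Inputs for CGI-SCH-S.** From the documents: 44.2 v 66.3 observed, and two-sided 0.05. Assumed, because the documents give nothing: an effect of 0.4 SD of the change score; ρ, the baseline to Day 84 correlation, 0.5 to 0.8; and k, the baseline SD divided by the Day 84 SD, 0.8 to 1.

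**Formula.** Variance of the unadjusted change comparison over the baseline-adjusted one:

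R = (1 + k² − 2ρk) / (1 − ρ²) = 1 + (k − ρ)² / (1 − ρ²)

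The gain is zero when k = ρ and grows as k moves above ρ. Unadjusted power is Φ(2.06 − 1.96) = 54.0%. Adjusted power is Φ(2.06 × √R − 1.96). The equivalent number of extra observed subjects in a pair of 110.5 is 110.5 × (R − 1).

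| k | ρ | R | Adjusted power | Gain (points) | Extra subjects |
|---|---|---|---|---|---|
| 1 | 0.5 | 1.333 | 66.2% | 12.2 | 36.8 |
| 1 | 0.7 | 1.176 | 60.8% | 6.8 | 19.5 |
| 1 | 0.8 | 1.111 | 58.4% | 4.4 | 12.3 |
| 0.9 | 0.5 | 1.213 | 62.1% | 8.1 | 23.6 |
| 0.9 | 0.7 | 1.078 | 57.1% | 3.1 | 8.7 |
| 0.9 | 0.8 | 1.028 | 55.1% | 1.1 | 3.1 |
| 0.8 | 0.5 | 1.120 | 58.7% | 4.7 | 13.3 |
| 0.8 | 0.7 | 1.020 | 54.8% | 0.8 | 2.2 |
| 0.8 | 0.8 | 1.000 | 54.0% | 0.0 | 0.0 |

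**Which rows are plausible.** Inclusion criterion 10 sets a BNSS floor and requires "stable single-blind placebo run-in and baseline BNSS total" scores, and criterion 11 caps positive symptoms. These rules do not mention CGI-SCH-S, but they restrict severity at entry. That would tend to make the Day 1 spread narrower than the Day 84 spread, so k below 1 and the smaller gains are plausible.

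**Check on a rounded 7-point scale.** Simulation with 1,500 trials per cell, scores rounded to 1–7, 15% missing at Day 84, dropout at random, an assumed 35/65 age split, equal correlations between visits and no site term. Power in %, at latent Day 84 SD 0.75 / 1.0:

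| k, ρ | CMH row mean scores | Day 84 ANCOVA | MMRM |
|---|---|---|---|
| 1, 0.5 | 40.7 / 48.1 | 54.7 / 60.9 | 55.6 / 61.3 |
| 1, 0.8 | 33.4 / 37.5 | 38.5 / 43.9 | 40.5 / 45.1 |
| 0.9, 0.7 | 36.4 / 41.9 | 40.9 / 46.5 | 41.2 / 47.9 |
| 0.8, 0.5 | 39.9 / 46.0 | 46.9 / 50.7 | 48.0 / 52.2 |
| 0.8, 0.8 | 31.7 / 41.1 | 33.6 / 41.0 | 33.9 / 41.7 |

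Rounding to whole points puts these powers below the closed form, but the pattern is the same. MMRM exceeds CMH by 0.6 to 14.9 points. The Day 28 and 56 ratings add only 0.3 to 2.0 points over a Day 84 ANCOVA, so nearly all the gain comes from the covariate. Type I error was 4.3% to 6.0% for both the row-mean CMH and the MMRM.

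**The case against.** The strongest reply is that the choice looks deliberate and sound. The SAP reserves the MMRM for continuous endpoints and gives a 7-point rating to a rank-type test. The test is valid, randomisation protects it from bias, the endpoint is secondary and uncontrolled for multiplicity, and every input to the size of the loss is assumed. All of this stands, and it is why the point is minor. It does not remove the point, because a baseline already collected could be used at little cost.

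A reader might infer more than the documents support:

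- **That baseline is ignored.** It is not: CGI-SCH-S is analysed as change, so Day 1 enters by subtraction.
- **That CGI-SCH-I suffers the same loss.** This is not shown. That score already rates change, and no document links it to Day 1 severity. If it depends on baseline only through CGI-SCH-S change and correlates 0.6 to 0.8 with it (assumed), the variance ratio is 1.00 to 1.19.
- **That not naming the CMH statistic halves the power.** In the simulation a general-association test had 18% to 23% power, against 32% to 48% for row mean scores. But the objective is superiority, which a test without direction does not address, and section 13.1.3.2 speaks of not controlling for multiple doses, which points to dose-by-dose comparisons. The gap is one of wording.
- **That restricting the test to observed Day 84 cases discards much.** The endpoint is defined at Day 84, the primary MMRM also uses observed data, and the earlier visits add almost nothing.

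**Conclusion.** The concern holds for CGI-SCH-S change, as a loss of precision and not as an error. Under the stated assumptions, adjusting for Day 1 CGI-SCH-S gains about 0 to 12 power points at two-sided 0.05 from a base of 54%. With k at 0.9 or below the closed-form gain is at most 8 points, and it vanishes where k equals ρ. The range rests on an assumed effect, correlation and SD ratio, so it shows direction and order of size only. The validity of the CMH, the primary test and the 82% power are not in question. Severity: minor.

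**What to change.** In SAP section 7.9.2, analyse change in CGI-SCH-S with the section 7.9.1 MMRM, taking Day 1 CGI-SCH-S as the baseline covariate. A Day 84 ANCOVA with the same covariate would give nearly the same gain. Keep the age-stratified CMH from the protocol as the sensitivity analysis, and specify it as row mean scores for each dose against placebo. For CGI-SCH-I, keep the CMH with the same specification; an analysis adjusted for Day 1 CGI-SCH-S is optional.

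The cost is SAP wording and some programming, with no new data. The model treats a 7-point scale as continuous. For CGI-SCH-S the simulation showed no inflation of type I error, and the retained CMH is a check. Because Protocol section 13.1.3.2 and the synopsis both name the CMH, the departure must be documented before unblinding.

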13.3 Determination of Sample Size

Assuming that the effect size is at least 0.4 for the 125 mg QD and 500 mg QD doses and that at least 85% of the 234 subjects complete the Day 84 assessment, the study has at least 82% power for at least 1 dose to be statistically-significant at the 0.10 level with correction for multiple doses.

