6.0 DETERMINATION OF SAMPLE SIZE

Assuming that the effect size is at least 0.4 for the as 125 mg QD and 500 mg QD doses and that at least 85% of the 234 subjects complete the Day 84 assessment, the study has at least 82% power for at least 1 dose to be statistically significant at the 0.10 level with correction for multiple doses.

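### The two CGI-SCH endpoints are tested on Day 84 observed cases alone, so earlier CGI scores from leavers go unused and the test is biased if dropout depends on response and differs by arm

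*SAP*

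**What the plan says.** SAP 7.9.2 sets the method for both CGI endpoints: "The change from Baseline on the CGI-SCH-S at Day 84, and the CGI-SCH-I score at Day 84 will be analyzed using a Cochran-Mantel-Haenszel test". It then adds: "This analysis will be stratified by age and performed using observed cases only". Protocol 13.1.3.2 has the same rule.

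For the primary endpoint, SAP 7.9.1 uses similar words inside a mixed model for repeated measures (MMRM): "Based on a Missing at Random Assumption, this analysis will be performed using observed case data only". There, a subject who leaves after Day 28 or Day 56 still contributes those visits. SAP 7.9.2 extends the MMRM to the other continuous change endpoints, then gives the CGI scales their own sentence.

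The other relevant provisions are:
- **Visits.** Protocol Appendix A schedules both CGI scales at Days 28, 56 and 84/ET. CGI-SCH-S is also scheduled at screening, Day -14 and Day 1.
- **Early termination.** An Appendix A footnote limits the CGI at early termination to subjects seen within 1 week of their last dose.
- **Windows.** SAP 7.2.2 assigns results to visits by windows that generally run between midpoints.
- **Sensitivity analyses.** The placebo-based pattern-mixture imputation and the ANCOVA on imputed data in SAP 7.9.1 are for the primary endpoint only.
- **COVID-19.** The blinded review in Protocol 13.1.3.2 names both CGI scales, but covers only remote or missing final assessments due to COVID-19.
- **Amendment.** SAP 7.14 lists no missing-data analysis for CGI.

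**The concern.** Similar wording has different consequences in the two analyses. Within an MMRM, using observed data is a likelihood analysis under MAR that draws on every visit. Within a single-visit CMH, it restricts the test to subjects who have a Day 84 value. No planned inferential CGI analysis uses Day 28 or Day 56. An early-termination score taken well before Day 84 falls in an earlier window and is also unused.

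The protocol foresees exits related to response: Section 7.6 lists unsatisfactory therapeutic response (item 7) and symptomatic deterioration (item 10). If such exits are more frequent in one arm, the remaining subjects in the two arms are selected differently, and the comparison can move in either direction. Global severity and global improvement are two named secondary objectives. They could then disagree with the primary result only because missing data were handled differently.

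**Working it through.** **Inputs from the documents.** Allocation is 52:52:52:78 (Protocol 2.0; the 2:2:2:3 ratio is in 8.3). Completion is "at least 85% of the 234 subjects complete the Day 84 assessment" (SAP 6.0). The level for the CGI tests is the two-sided default in SAP 7.1, which "will be assessed at α =0.05 significance level unless otherwise stated"; 7.9.2 states no other level.

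**The plan's own figure.** Protocol 13.3 starts from "Assuming that the effect size is at least 0.4 for the 125 mg QD and 500 mg QD doses" and concludes that "the study has at least 82% power for at least 1 dose to be statistically-significant at the 0.10 level with correction for multiple doses". This concerns the primary endpoint; no power is stated for CGI.
- Completers: 52 × 0.85 = 44.2 per dose arm, and 78 × 0.85 = 66.3 on placebo.
- Noncentrality: 0.4 / √(1/44.2 + 1/66.3) = 2.060.
- Holm's first step is one-sided 0.10/2 = 0.05. Power for one dose is Φ(2.060 − 1.645) = 66.1%.
- The two comparisons share placebo, so their correlation is (1/66.3)/(1/44.2 + 1/66.3) = 0.4. Power for at least one dose is 82.8%, which agrees with the stated figure.

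**How many are dropped.** At most 0.15 × 234 = 35.1 subjects: 7.8 per dose arm and 11.7 on placebo. A leaver is kept if an early-termination CGI falls in the Day 84 window. That window opens at about Day 70 if the CGI visits define the midpoint, (56 + 84)/2, or Day 77 if all visits do, (70 + 84)/2.

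**Bias of the completers' comparison.** The documents give no CGI distribution, visit correlation or dropout pattern by arm, so the following are assumptions. The comparison is 52 vs 78, with a standardised continuous score (lower is better) at three post-baseline visits and adjacent-visit correlation 0.7. Dropout is monotone, with log-odds rising 0.5 or 1.0 per SD of the last score. There were 6,000 replicates per scenario. Bias is shown at a true effect of 0.4 SD; rejection is one-sided in favour of drug, under no effect, at nominal 0.025. Paired entries are for slopes 0.5 and 1.0.

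| Dropout, drug/placebo | Bias, completers (SD) | Bias, MAR using Days 28 and 56 (SD) | Rejection, completers |
|---|---|---|---|
| 15% / 15% | 0.000 to 0.001 | 0.000 to 0.001 | – |
| 10% / 20% | +0.032; +0.060 | −0.002; 0.000 | 0.016; 0.012 |
| 20% / 10% | −0.031; −0.056 | 0.003; 0.001 | 0.035; 0.051 |

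Against an effect of 0.4, the bias in the 10%/20% case is 0.032/0.4 = 8% to 0.060/0.4 = 15%. The standard error is 0.189 to 0.195 for completers and 0.186 to 0.190 for the MAR estimator. The largest bias is therefore about 0.06/0.19 ≈ 0.3 of a standard error, and the gain in precision is only 1 to 3%.

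Adding the two mirrored tails gives the approximate two-sided error: 0.035 + 0.016 = 0.051 at slope 0.5, and 0.051 + 0.012 = 0.063 at slope 1.0.

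**The CMH itself.** A second simulation used a 7-point score and the stratified mean-score CMH, with no true effect. Correlation was 0.5 to 0.8, slope 1 per SD, dropout 15% unless stated, with 4,000 runs per case. Two-sided error at nominal 0.05 was:

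| Dropout pattern | Observed-case CMH | MAR estimator |
|---|---|---|
| Random | 0.046–0.048 | 0.048–0.051 |
| Response-dependent, same in both arms | 0.049–0.051 | 0.050–0.051 |
| Poor responders leave on drug, random on placebo | 0.064–0.082 | 0.049–0.054 |
| Same slope, 25% on drug vs 8.3% on placebo | 0.068–0.090 | 0.057 |
| Poor responders leave on drug, good responders on placebo | 0.105–0.181 | 0.049–0.055 |

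Observed-case bias in the last three rows runs from −0.07 to −0.21 points. For the MAR estimator it stays within about 0.015 points.

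**The case against.** The strongest reply is that little depends on this. These are two phase 2 secondary endpoints without multiplicity control. The primary endpoint has its MMRM and a placebo-based sensitivity analysis. Subjects enter symptomatically stable, both cited exit criteria require an unacceptable risk to the subject, and nothing in the documents predicts unequal exits. All of that stands. It limits the weight of the point but does not give these endpoints a missing-data analysis.

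Several stronger readings are tempting, and the documents and calculations do not support them:
- **That the test is valid only if missingness is unrelated to response.** Equal response-driven dropout of 15% gave bias of 0.000 to 0.001 SD, and the same mechanism in both arms left the CMH error at 0.049 to 0.051. A difference between arms is also needed.
- **That 35 subjects will be lost.** At least 85% completing makes 35 a ceiling, and some early-termination scores fall in the Day 84 window.
- **That every dropped subject has usable CGI data.** Those who leave before any post-baseline CGI have no CGI-SCH-I and only pre-treatment CGI-SCH-S.
- **That the error doubles.** The move from 0.025 to 0.051 is in one tail. The tests are two-sided, and the other tail shrinks.
- **That error near 0.18 is to be expected.** It needs opposite dropout mechanisms in the two arms, for which the documents give no basis.
- **That the planned imputation can simply be reused.** It is placebo-based and built for PANSS NSFS; a by-arm MAR model for an ordinal score is a different model.

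**Conclusion.** The point holds as a specific, modest weakness. The CGI tests discard post-baseline scores that the trial collects, and they are biased when dropout depends on response and differs by arm. With 10% against 20% dropout, correlation 0.7 and slopes of 0.5 to 1.0 per SD, the bias is about 0.03 to 0.06 SD in either direction. Two-sided error is then about 0.05 to 0.06 against 0.05. One tail rises to 0.035–0.051 and the other falls to 0.012–0.016, against 0.025 each. More extreme differences between arms give more. A MAR analysis using Days 28 and 56 removes nearly all of the bias when dropout depends on the observed scores, as simulated here.

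The size rests on assumptions that the documents neither supply nor contradict, including the use of the primary endpoint's 0.4 as the CGI effect. A reader might infer that the trial's main result is in doubt. It is not: the primary analysis does not use these tests.

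**What to change.** Keep the age-stratified observed-case CMH as Protocol 13.1.3.2 states it. Before unblinding, add to SAP 7.9.2 a pre-specified MAR analysis of both CGI scales using Days 28, 56 and 84. Choose one of two forms:
- a repeated-measures model: MMRM for CGI-SCH-S change and an ordinal repeated-measures model for CGI-SCH-I; or
- multiple imputation of missing Day 84 scores by arm, from Day 1, 28 and 56 CGI-SCH-S and Day 28 and 56 CGI-SCH-I, with the age-stratified mean-score differences combined by Rubin's rules.

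State that interpretation of the two CGI objectives rests on the MAR analysis where it and the CMH differ.

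No new data are needed. The cost is a new model to specify and program for a 7-point ordinal score. It will recover little for subjects who leave before Day 28.
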